2.7.3 Laboratory data

Each laboratory parameter, evaluations will be summarized by visit and actually received treatment group by presenting summaries (n, mean, standard deviation, median, minimum and maximum) for actual and change from baseline values. The summary will be provided separately for biochemistry and hematology laboratory parameters. Central laboratory data will be used for the summaries.

Shift tables based on the standard ranges for each laboratory parameters will be provided by treatment group at each visit to present incidence of transitions from a baseline high, normal or low laboratory value to a post-baseline high, normal or low value.

The number and percentage of patients with clinically notable laboratory results after baseline will be presented in accordance with Table 2-6.

Table 2-6 Clinically notable laboratory values and vital signs

Hematology

Hematocrit	>50% increase, >20% decrease
Hemoglobin	>50% increase, >20% decrease
Platelet count	>75% increase, >50% decrease
RBC Count	>50% increase, >20% decrease
WBC count	>50% increase, >50% decrease

Blood chemistry

Alkaline phosphatase	>100% increase
ALT (SGPT)	>150% increase
AST (SGOT)	>150% increase
BUN	>50% increase
Calcium	>10% increase, >10% decrease
Chloride	>10% increase, >10% decrease
Creatinine	>50% increase
Potassium	>20% increase, >20% decrease
Total bilirubin	>100% increase
Uric acid	>50% increase

Patients with liver enzymes (ALT/AST and CPK) falling within predefined categories of elevations and persistent elevations will be summarized by treatment group in accordance with the Table 2-7 for the double-blind period.

Descriptive summaries will be provided by presenting count and percentage of patients with each type of Liver event in addition to graphical summaries, as applicable.

Table 2-7 Liver Event and Laboratory Trigger Definitions

	Definition/ threshold
LIVER LABORATORY TRIGGERS	
 • 3 x ULN < ALT / AST ≤ 5 x ULN • 1.5 x ULN < TBL ≤ 2 x ULN
LIVER EVENTS	
 • ALT or AST > 5 × ULN • ALP > 2 × ULN (in the absence of known bone pathology) • TBL > 2 × ULN (in the absence of known Gilbert syndrome) • ALT or AST > 3 × ULN and INR > 1.5

	
 • Potential Hy's Law cases (defined as ALT or AST > 3 × ULN and TBL > 2 × ULN [mainly conjugated fraction] without notable increase in ALP to > 2 × ULN) • Any clinical event of jaundice (or equivalent term) • ALT or AST > 3 × ULN accompanied by (general) malaise, fatigue, abdominal pain, nausea, or vomiting, or rash with eosinophilia • Any adverse event potentially indicative of a liver toxicity*
--	--

*These events cover the following: hepatic failure, fibrosis and cirrhosis, and other liver damage-related conditions; the non-infectious hepatitis; the benign, malignant and unspecified liver neoplasms
TBL: total bilirubin; ULN: upper limit of normal

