4.2 Exclusion criteria

Patients fulfilling any of the following criteria are not eligible for inclusion in this study. No additional exclusions may be applied by the investigator, in order to ensure that the study population will be representative of all eligible patients.

1. Known history of chronic HF prior to randomization
2. Cardiogenic shock within the last 24 hours prior to randomization
3. Persistent clinical HF at the time of randomization
4. Coronary artery bypass graft (CABG) performed or planned for index MI
5. Clinically significant right ventricular MI as index MI
6. Symptomatic hypotension at screening or randomization
7. Patients with a known history of angioedema
8. Stroke or transient ischemic attack within one month prior to randomization
9. Known or suspected bilateral renal artery stenosis
10. Clinically significant obstructive cardiomyopathy

11. Open-heart surgery performed within one month prior to randomization or planned cardiac surgery within the 3 months after randomization
12. eGFR < 30 ml/min/1.73 m² as measured by the Modification of Diet in Renal Disease (MDRD) formula at screening
13. Serum potassium > 5.2 mmol /L (or equivalent plasma potassium value) at randomization
14. Known hepatic impairment (as evidenced by total bilirubin > 3.0 mg/dL or increased ammonia levels, if performed), or history of cirrhosis with evidence of portal hypertension such as esophageal varices
15. Previous use of LCZ696 or Entresto™
16. Use of other investigational drugs within 30 days prior to screening
17. History of hypersensitivity to the study drugs or drugs of similar chemical classes
18. Known intolerance or contraindications to study drugs or drugs of similar chemical classes including ACE inhibitors, ARB or NEP inhibitors
19. Patients taking medications prohibited by the protocol that cannot be discontinued for the duration of the study
20. History of malignancy of any organ system (other than localized basal cell carcinoma of the skin) within the past 3 years with a life expectancy of less than 1 year.
21. Any surgical or medical condition which might significantly alter the absorption, distribution, metabolism, or extraction of study drug at investigators' discretion.
22. History or evidence of drug or alcohol abuse within the last 12 months

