6.5.4 Laboratory evaluations

A central laboratory will be used for analysis of most specimens collected. Details on the collection, shipment of samples and reporting of results by the central laboratory are provided to investigators in the laboratory manual.

Clinically notable laboratory findings are defined in [Appendix 1](#).

Complete central laboratory evaluations (hematology and blood chemistry) for the assessment of safety in this study will be performed at Visits 101, 104, 106, 108, 111, 114, 117, annually thereafter, and end of study (199). Abbreviated laboratory central evaluations will be performed at all interim visits as indicated in [Table 6-1](#).

In addition to the required central laboratory assessments, a local laboratory may be used for the assessment of potassium, creatinine and eGFR during the screening period and dose titration period as indicated in [Table 6-1](#). The results from the local laboratory will be allowed

to make decisions regarding randomization, study drug administration and dose titration/dose level adjustments, and will be recorded in the eSource/source documents at the study sites. In addition, local laboratory assessments of potassium, creatinine and eGFR may be performed on an as-needed basis to monitor tolerability to study drug and dose adjustments at scheduled or unscheduled visits during the treatment epoch. If local laboratory assessments are not possible or it will take longer to receive results than through the central laboratory assessment, the central laboratory may be used instead of local labs to make decisions regarding the study drug dosing.

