7.1 Adverse events

An adverse event (AE) is any untoward medical occurrence (e.g., any unfavorable and unintended sign [including abnormal laboratory findings], symptom or disease) in a patient or clinical investigation patient after providing written informed consent for participation in the study until the end of study visit. Therefore, an AE may or may not be temporally or causally associated with the use of a medicinal (investigational) product.

In addition, all reports of intentional misuse and abuse of the product are also considered an adverse event irrespective if a clinical event has occurred.

Adverse events of special interest (angioedema, hyperkalemia, hypotension, renal impairment, cognitive impairment, hepatotoxicity, hypersensitivity, malignancy, pregnancy and exposure during breast feeding, statin-related adverse events), along with all other AE and SAEs will be summarized and sent to the DMC for periodic safety reviews during the trial. The occurrence of adverse events must be sought by non-directive questioning of the patient at each visit during the study. Adverse events also may be detected when they are volunteered by the patient during or between visits or through physical examination findings, laboratory test findings, or other assessments.

Abnormal laboratory values or test results constitute adverse events only if they fulfill at least one of the following criteria:

- they induce clinical signs or symptoms,
- they are considered clinically significant,
- they require therapy.

Clinically significant abnormal laboratory values or test results must be identified through a review of values outside of normal ranges/clinically notable ranges, significant changes from baseline or the previous visit, or values which are considered to be non-typical in patient with underlying disease. Investigators have the responsibility for managing the safety of individual patient and identifying adverse events. Alert ranges for laboratory and other test abnormalities are included in [Appendix 1](#).

[REDACTED]

Adverse events must be recorded in the Adverse Events CRF under the signs, symptoms or diagnosis associated with them, accompanied by the following information:

- the severity grade:
 - mild: usually transient in nature and generally not interfering with normal activities
 - moderate: sufficiently discomforting to interfere with normal activities
 - severe: prevents normal activities
- its relationship to the study treatment:
 - Yes
 - No

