
The HOPE Investigators: Effects of an angiotensin-converting-enzyme inhibitor, ramipril, on cardiovascular events in high-risk patients. *N Engl J Med* 2000;342:145-53.

van Diepen D, Chen A, Wang, T, et al. Influence of heart failure symptoms and ejection fraction on short- and long-term outcomes for older patients with non-ST-segment elevation myocardial infarction. *Am Heart J* 2014;167:267-273.e1.

13 Appendix 1: Clinically notable laboratory values and vital signs

Clinically notable laboratory abnormalities for selected tests based on a percent change from baseline:

Hematology

Hematocrit	>50% increase, >20% decrease
Hemoglobin	>50% increase, >20% decrease
Platelet count	>75% increase, >50% decrease
RBC Count	>50% increase, >20% decrease
WBC count	>50% increase, >50% decrease

Blood Chemistry

Alkaline phosphatase	>100% increase
ALT (SGPT)	>150% increase
AST (SGOT)	>150% increase
BUN	>50% increase
Calcium	>10% increase, >10% decrease
Chloride	>10% increase, >10% decrease
Creatinine	>50% increase
Potassium	>20% increase, >20% decrease
Total bilirubin	>100% increase
Uric acid	>50% increase

14 Appendix 2: Liver event and Laboratory trigger Definitions and Follow-up Requirements

Table 14-1 Liver Event and Laboratory Trigger Definitions

	Definition/ threshold

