- Consider down-titration of study drug, according to investigator's medical judgment.

Serum potassium greater than or equal to 5.5 and less than 6.0 mmol/L (mEq/L)*

[figure not shown]
[figure not shown]
- Confirm serum potassium concentration in a non-hemolyzed sample
- Consider down-titration or temporarily discontinue background therapy of mineralocorticoid antagonists (if they are believed to be the most likely cause of hyperkalemia).
- Apply all measures outlined for serum potassium > 5.3 and < 5.5 mmol/L*
- Repeat serum potassium measurement after 2-3 days
- If serum potassium < 5.5 mmol/L*, consider resumption of study drug at lower dose with repeat serum potassium within 5 days

[figure not shown]
[figure not shown]
Serum potassium greater than or equal to 6.0 mmol/L (mEq/L)*

[figure not shown]
[figure not shown]
- Immediately discontinue study drug
 - Confirm serum potassium concentration in a non-hemolyzed sample
 - Urgently evaluate patient and treat hyperkalemia as clinically indicated
 - Apply all measures outlined for serum potassium > 5.3 and < 6.0 mmol/L (mEq/L)*

[figure not shown]
No resumption of study drug without individualized case discussion with and permission from Novartis medical monitor or his/her designee.

*Or equivalent plasma potassium value

LCZ696 with atorvastatin or other statins. Further, in order to achieve the target dose in the early phase post AMI, for patients who have not titrated to the target dose level 3 by week 4, an unscheduled dose titration visit on or about week 6 is also recommended. Finally, some minor changes were also made to clarify the valsartan bridging procedure on day 1 post randomization, and to correct typographical errors and inconsistencies in the protocol. There is no impact of this amendment on the study population or the main analysis of the study results.

The main changes in this amendment are:

[REDACTED]

[REDACTED]

Section 4.1 Inclusion criteria

- Inclusion criteria #3 was updated to clarify that patients with clinical presentation thought to be related to Takotsubo cardiomyopathy are also not eligible.
- Inclusion criteria #4 was updated to add diuretics, vasodilators, vasopressors and/or inotropes as intravenous treatment required for pulmonary congestion. A footnote was also added clarifying the index MI with LV systolic dysfunction **and/or** pulmonary congestion.

Section 4.2 the following exclusion criteria were updated or added

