2.7.4 Other safety data

2.7.4.1 Vital signs

Sitting systolic blood pressure (SBP), sitting diastolic blood pressure (DBP) and Sitting pulse pressure (PP) will be descriptively summarized by presenting summaries (n, mean, standard deviation, median, minimum, maximum) of actual value and change from baseline values for each scheduled assessment visit and treatment group.

The number and percentage of patients with clinically notable vital signs changes from baseline will be presented. Clinically notable vital sign results are provided in Table 2-8 below.

Table 2-8 Clinically notable changes in vital signs

Vital Sign (unit)	Clinically notable criteria
Weight (kg)	decrease > 7% from Baseline increase > 7% from Baseline
Sitting systolic blood pressure (mmHg)	<=90 and decrease from baseline >=20 >=180 and increase from baseline >=20
Sitting diastolic blood pressure (mmHg)	<=50 and decrease from baseline >=15 >=105 and increase from baseline >=15
Pulse (bpm)	<=50 and decrease from baseline >=15 >=120 and increase from baseline >=15

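### SAP Table 2-6 counts potassium as notable only on a change of more than 20% from baseline, so it can miss values at the protocol's own action levels; a count at those levels should be added

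*SAP*

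**What the plan says.** **Notable-value rule.** Protocol Appendix 1 introduces its list as "Clinically notable laboratory abnormalities for selected tests based on a percent change from baseline". SAP Table 2-6 carries the list over, and the potassium line in both documents reads ">20% increase, >20% decrease". SAP 2.7.3 then states: "The number and percentage of patients with clinically notable laboratory results after baseline will be presented in accordance with Table 2-6". Central laboratory data are used.

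**Use at sites.** Protocol 7.1 tells investigators: "Alert ranges for laboratory and other test abnormalities are included in" Appendix 1. Protocol 6.5.4 asks that values beyond a notable boundary be assessed for adverse events.

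**Absolute levels.** Exclusion criterion 13 in protocol 4.2 is "Serum potassium > 5.2 mmol /L (or equivalent plasma potassium value) at randomization", so a baseline of 5.0 is eligible. Appendix 5 requires confirmation of any value above 5.3 mmol/L, calls 5.5 to below 6.0 a range of concern and 6.0 or above potential danger, and stops study drug in the band headed "Serum potassium greater than or equal to 6.0 mmol/L (mEq/L").

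**Other potassium outputs.** SAP 2.7.3 also plans summary statistics (including the maximum) for actual values and changes, and low/normal/high shift tables at each visit. SAP 2.7.1.1 analyses hyperkalemia as an adverse event of special interest, retrieved through MedDRA searches.

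**Blood pressure.** The low-side systolic criterion in SAP Table 2-8 is "<=90 and decrease from baseline >=20".

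**The concern.** A relative-change rule makes the flagging threshold rise with the baseline. Patients who enter closest to the level at which the protocol acts therefore need the highest value before they are counted, and a patient with a low baseline is counted at a value that would still satisfy the entry criterion. The table headed as clinically notable potassium thus answers a different question from the one Appendix 5 poses.

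The safety and tolerability of LCZ696 against ramipril is a stated secondary objective, and hyperkalemia is a named event of special interest. A reader of the study report will want to know how many patients in each arm reached 5.5 or 6.0 mmol/L, and no readable table in the SAP says so.

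**Working it through.** **Inputs.** Rule: change strictly greater than 20% (SAP Table 2-6, protocol Appendix 1). Levels: >5.3, ≥5.5 and ≥6.0 mmol/L (protocol Appendix 5). Entry limit: 5.2 mmol/L (protocol 4.2). The plan states no figure on this point, so there is none to reproduce.

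**Formula.** An increase is notable only if (follow-up − baseline)/baseline > 0.20, that is, if follow-up > 1.2 × baseline.

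**Individual cases** (no assumption needed):

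| Baseline | Follow-up | Change | Counted? |
|---|---|---|---|
| 5.0 | 6.0 | 1.0/5.0 = 20.0% | no |
| 5.2 | 6.2 | 1.0/5.2 = 19.2% | no |
| 4.6 | 5.5 | 0.9/4.6 = 19.6% | no |
| 4.5 | 5.4 | 0.9/4.5 = 20.0% | no |
| 4.0 | 4.9 | 0.9/4.0 = 22.5% | yes |

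**Value that must be exceeded, by baseline:** 4.0 → 4.80; 4.4 → 5.28; 4.6 → 5.52; 5.0 → 6.00; 5.2 → 6.24.

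**Baselines from which a given level is missed:** 5.5/1.2 = 4.58, so a value of 5.5 is missed from about 4.6 upward; 6.0/1.2 = 5.0, so a value of exactly 6.0 is missed from 5.0 upward.

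**How often (assumed distributions only).** The documents give no potassium distribution, so any share is an illustration. Two sets of bivariate normal assumptions were tried, each with one follow-up value per patient and baseline capped at 5.2:

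- Baseline mean 4.1–4.3 (SD 0.40–0.45), follow-up mean 4.4–4.6 (SD 0.45–0.50), correlation 0.3–0.5. Over four parameter sets, 20–51% of values ≥5.5 and 5–15% of values ≥6.0 were missed, and 80–90% of flagged rises were at or below 5.3.
- Baseline mean 4.2–4.4, SD 0.4–0.5, mean shift 0–0.2, correlation 0.2–0.6, rounded to 0.1. About 10–52% of values ≥6.0 were missed (SD 0.5 scenarios, where such values are frequent enough to estimate), and 79–99% of flagged rises were at or below 5.3.

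The share missed at 6.0 runs from 5% to 52% across reasonable inputs. That is too unstable to quote as a property of this trial. Table 2-6 also counts patients over many visits, which a single follow-up value does not represent.

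**Do the other outputs supply the count?** The shift tables have three categories, so 5.4 and 6.5 fall together whenever both exceed the laboratory's upper limit. The summary maximum is one value per visit and arm. The special-interest analysis counts reported terms, not measured levels.

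**Systolic pressure, Table 2-8.** From a baseline of 100 mmHg, 81 is a fall of 19 and is not counted. From 109, 90 is a fall of 19 and is not counted. From 110 or more, reaching 90 already means a fall of at least 20. The gap is therefore confined to baselines of 100–109, which protocol 4.1 allows only for patients who received an ACE inhibitor or ARB in the preceding 24 hours. The uncounted values run from 81 to 90, depending on baseline.

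**The case against.** The strongest reply is that Table 2-6 is a general notable-change table and was never meant to measure hyperkalemia. Hyperkalemia has its own analysis in SAP 2.7.1.1, with crude percentages, exposure-adjusted rates and Kaplan-Meier estimates for selected events. Protocol 6.5.4 requires an adverse event entry when a laboratory abnormality leads to a dose adjustment or needs treatment, so a stop at 6.0 should reach the event data whatever the baseline. Appendix 5 requires confirmation of every value above 5.3, and protocol 7.1 also directs sites to out-of-range values and changes from the previous visit. The shift tables would show a move to high if 6.0 exceeds the laboratory limit.

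Most of this stands, and it rules out several stronger readings that a reader might infer:

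- *That hyperkalemia is assessed by the 20% rule.* It is not; only the notable-value count is.
- *That the count consists mostly of normal values.* The documents give neither a potassium distribution nor a laboratory range, and 5.3 is an action level, not a normal limit.
- *That the rule hides a difference between arms.* The calculations contain no comparison of arms.
- *That sites would overlook high values.* The confirmation and reporting duties above say otherwise.
- *That local results are lost.* Protocol 6.5.4 says that local results used for dosing decisions "will be recorded in the eSource/source documents at the study sites", so the number itself may not reach the tables, but an event that changed the dose should still be reported.

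What the reply does not supply is a count of patients at the protocol's own levels. Between 5.5 and 6.0, Appendix 5 mostly asks the investigator to consider action, so an adverse event entry is less certain there. On blood pressure, Appendix 4 sets no numeric level, the minimum is tabulated and hypotension is an event of special interest, so that gap is minor.

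**Conclusion.** The concern holds as a gap in one descriptive safety table. The rule and the single-patient cases follow from the documents without assumption: eligible patients can reach 5.5 or 6.0 mmol/L without being counted, while a rise to 4.9 can be. The size of the gap in this trial cannot be stated; the simulated shares are illustrations that vary widely with the inputs.

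No efficacy inference is affected, and the special-interest analysis remains in place. SAP 2.7 is readable throughout and holds no such count. The text between SAP 2.9 and 2.14 is blacked out, so a table there cannot be excluded. The change is worth making because it costs little and gives a safety comparison on the scale that the protocol itself uses.

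**What to change.** 1. In SAP 2.7.3, accompany the potassium line of Table 2-6 with the number and percentage of patients by arm who have any post-baseline central laboratory potassium >5.3, ≥5.5 and ≥6.0 mmol/L, overall and by visit. These are the existing Appendix 5 levels; no new threshold is introduced.
2. As a minor addition, show in Table 2-8 the number of patients with systolic pressure ≤90 mmHg without the change condition, next to the current criterion.
3. Ask the sponsor to reconcile the potassium alert range in Appendix 1 with the bands in Appendix 5, or to explain why they differ. Which of the two is right is for the sponsor to settle.

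The cost of the first two is a few lines of SAP wording, one new table and one extra row, all from data already collected. They are descriptive and use no alpha. The third is a query to the sponsor.

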2.7.4 Other safety data

2.7.4.1 Vital signs

Sitting systolic blood pressure (SBP), sitting diastolic blood pressure (DBP) and Sitting pulse pressure (PP) will be descriptively summarized by presenting summaries (n, mean, standard deviation, median, minimum, maximum) of actual value and change from baseline values for each scheduled assessment visit and treatment group.

The number and percentage of patients with clinically notable vital signs changes from baseline will be presented. Clinically notable vital sign results are provided in Table 2-8 below.

Table 2-8 Clinically notable changes in vital signs

Vital Sign (unit)	Clinically notable criteria
Weight (kg)	decrease > 7% from Baseline increase > 7% from Baseline
Sitting systolic blood pressure (mmHg)	<=90 and decrease from baseline >=20 >=180 and increase from baseline >=20
Sitting diastolic blood pressure (mmHg)	<=50 and decrease from baseline >=15 >=105 and increase from baseline >=15
Pulse (bpm)	<=50 and decrease from baseline >=15 >=120 and increase from baseline >=15

